#### **5.4.1.2. Between groups assessment**

95% CIs for differences between vaccine groups will be provided according to Miettinen and Nurminen method [[Miettinen](#), 1985].

## 5.4.2. Additional considerations

### 5.4.2.1. Exclusion of implausible solicited Adverse Event

Some local and systemic adverse events will be directly measured by the subject and will not be subject to a reconciliation process, even if they are biologically implausible. Therefore, these implausible measurements will be removed from the analysis but included in listings. Implausible measurements are summarized in the table below:

**Table 8      Implausible Solicited Adverse Events**

Parameter	Implausible measurements
Body temperature	$\leq 33^{\circ}\text{C}$ or $\geq 42^{\circ}\text{C}$
Erythema	Measurements $< 0$ mm or $\geq 450$ mm
Induration	Measurements $< 0$ mm or $\geq 250$ mm
Swelling	Measurements $< 0$ mm or $\geq 250$ mm

### 5.4.2.2. Duration of Solicited Adverse Events

Duration of a solicited adverse event will be calculated as follows:  $\text{end date} - \text{start date} + 1$ . The duration will be derived assuming that the solicited adverse event occurred continuously from the first day to the last day the event was reported regardless of how many days the event was documented in between.

Statistics (i.e. mean, median minimum, maximum, quartiles) on the duration in days of solicited local (administration site) and systemic adverse events post vaccination will be reported by timepoint and overall, by each solicited reaction, for each vaccine group.

Statistics (i.e. mean, median minimum, maximum, quartiles) on the duration in days of solicited local (administration site) and systemic adverse events post any vaccination will be reported by each solicited reaction, for each vaccine group.

Statistics (i.e. mean, median minimum, maximum, quartiles) on the day of onset of solicited local (administration site) and systemic adverse events post vaccination will be provided by timepoint, by each solicited reaction, for each vaccine group.

Statistics (i.e. mean, median minimum, maximum, quartiles) on the day of onset of solicited local (administration site) and systemic adverse events post any vaccination will be provided by each solicited reaction, for each vaccine group.

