The use of rMenB+OMV NZ in infants was associated with frequent reports of reactogenicity and especially of local reactions, although most were of mild or moderate severity and transient. Consistent with the extensive safety data collected in the vaccination campaigns with other OMV-based vaccines, increased rates of fever were associated with rMenB+OMV NZ vaccination in the infant population, especially when given concomitantly with routine vaccines. As the fever resolved soon after vaccination and these higher rates were not associated with an increase in medically attended adverse events (AEs) or an increase in febrile seizure risk, these data overall supported giving rMenB+OMV NZ either concomitantly with or without routine pediatric vaccines. Additionally, the use of prophylactic acetaminophen (paracetamol) given at the time of vaccination and/or closely thereafter has shown to decrease fever and reactogenicity in infants, without interfering with the antibody response to rMenB+OMV NZ, nor to the concomitantly administered routine vaccines (DTPa-HBV-IPV/Hib and PCV7) [Prymula, 2014].

Please refer to the current Investigator Brochure for information regarding the pre-clinical and clinical studies and the epidemiological information of rMenB+OMV NZ (*Bexsero*).

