5.6.16.1.1. Subject diary alerts

The subject's parent(s)/LAR(s) will receive daily reminders via the Subject Diary device's in-built audio-visual alarms to alert the user to complete the diary during the post vaccination period, which is from Day 1 to Day 7 after Visits 1, 2 and 3 (or until the solicited AE resolves) and from Day 1 to Day 30 after Visit 5.

The Subject Diary system will also allow for regular alerts to be issued via email to site staff indicating where subjects may need to be contacted due to:

- Non-compliance (i.e. failing to enter or transmit diary data),
- Reporting of any severe solicited reactions,
- Subject experienced any AE that required hospitalization or visit to the emergency room or medically attended events that were of concern to the parents/LAR(s).

Sites must assess these alerts when received and contact subjects as necessary. Please refer to Section 8.2 on the premature withdrawals from the study and Section 7.2.3 on the evaluation of AEs for guidance on necessary action in the event of one of these alerts.

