**Table 7      Grading of Solicited Systemic Adverse Events for All Subjects**

Adverse Events	Grading of Severity			
	Grade 0	Mild	Moderate	Severe
Decreased eating	None	Eating less than normal for 1 - 2 feeds/ meals	Missed 1 or 2 feeds / meals	Missed more than 2 feeds/ meals
Increased sleepiness	None	Shows an increased drowsiness	Sleeps through feeds/ meals	Sleeps most of the time and it is hard to arouse him/her
Vomiting / throwing up	None	1-2 times in 24 hours	3 – 5 times in 24 hours	6 or more times in 24 hours or requires intravenous hydration
Loose stools / Diarrhea	Fewer than 2 loose stools in 24 hours	2 - 3 loose stools in 24 hours	4 - 5 loose stools in 24 hours	6 or more loose stools in 24 hours or requires intravenous hydration
Irritability	None	Requires more cuddling and is less playful than usual	More difficult to settle	Unable to console
Persistent / continuous crying	None	Crying less than 1 hour	Crying for 1 up to 3 hours	Crying for 3 or more hours
Rash 	0	1-50 lesions	51-150 lesions	>150 lesions
Parotid/salivary gland swelling 	None	Swelling without difficulty moving the jaw	Swelling with difficulty moving the jaw	Swelling with accompanying general symptoms
Fever 	<38.0°C (<100.4°F)	≥38.0 - 38.9°C (≥100.4 – 102.1°F)	≥39.0 - 39.9°C (≥102.2 – 103.9°F)	≥40.0°C (≥ 104.0°F)

Rash and parotid/salivary gland swelling will be recorded only after receiving the MMR and VV vaccines at 12 months of age at Visit 5 (Day 301). These specific systemic AEs, along with fever, will be recorded for 30 days following the MMR and VV vaccine administration.

Preferred locations for measuring temperature are the rectum for subjects <12 months of age and the axilla for subjects ≥12 months of age. Body temperature is to be recorded daily, ideally at the same time each day.

Frequencies and percentages of subjects (with 95% CI; [Frank, 2009; Clopper, 1934]) experiencing each AE will be presented for each symptom severity. Summary tables showing the occurrence of any local or systemic AE overall and at each time point will also be presented.

Post-vaccination solicited AE reported from Day 1 to Day 7 will be summarized for the interval Day 1-7 (and Day 1-3, Day 4-7 if needed) by maximal severity and by vaccine

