group, excluding the 30-minute measurement, which will be summarized separately. For MMR and VV-specific solicited systemic AEs (parotid/salivary gland swelling, fever, rash) collected after Visit 5 (30 minutes through Day 30 post vaccination), the study period will be divided into the following intervals: 6 hours through Day 7, Day 8 through Day 30.

The severity of solicited local AEs (administration site events), including redness at injection site, swelling of skin at injection site, and hardness of skin at injection site will be summarized according to categories based on linear measurement: None (0 mm); Mild (1 mm to 25 mm); Moderate (26 mm to 50 mm); Severe (> 50mm).

Injection site tenderness and systemic reactions (except fever) occurring up to 7 days after each vaccination will be summarized according to “mild”, “moderate” or “severe”.

Fever, derived from measured body temperature ( $\geq 38.0^{\circ}\text{C}/100.4^{\circ}\text{F}$ ), will be summarized according to “Grade 0 (none)” ( $< 38.0^{\circ}\text{C}$ ), “mild” ( $\geq 38.0 - 38.9^{\circ}\text{C}$ ), “moderate” ( $\geq 39.0 - 39.9^{\circ}\text{C}$ ) and “severe” ( $\geq 40.0^{\circ}\text{C}$ ).

Each solicited local (administration site) and systemic AE will also be further summarized as “none” versus “any” (for fever the latter will be  $\geq 38.0^{\circ}\text{C}/100.4^{\circ}\text{F}$ ).

Use of antipyretics and analgesics will be summarized by type of use (prophylactic versus treatment) and percentage of subjects (with 95% CI) reporting use.

Body temperature will be summarized by  $0.5^{\circ}\text{C}$  increments from  $36.0^{\circ}\text{C}$  up to  $\geq 40^{\circ}\text{C}$  and will be broken down according by route of measurement, if applicable. Frequencies and percentages of subjects (with 95% CI) with temperatures  $\geq 38.0^{\circ}\text{C}$  and temperatures  $\geq 40.0^{\circ}\text{C}$  will also be presented.

Descriptive summary statistics will be provided for subgroups gender, race, and ethnic origin.

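### The SAP's first-to-last-day duration rule reports separate episodes as one long event, which can matter for fever, rash and parotid/salivary gland swelling collected over 30 days after dose 4

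*SAP*

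**What the plan says.** SAP 5.4.2.2 takes the end date minus the start date plus one, "assuming that the solicited adverse event occurred continuously from the first day to the last day the event was reported", and it does so however few of the intervening days carry a report of the event. It has no rule for separating episodes, no maximum gap and no count of days with the event. Mean, median, minimum, maximum and quartiles of this duration are "reported by timepoint and overall, by each solicited reaction, for each vaccine group".

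The collection window depends on the event and the dose:

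- **Fever, rash and parotid/salivary gland swelling after dose 4.** The footnote to SAP Table 7 says: "These specific systemic AEs, along with fever, will be recorded for 30 days following the MMR and VV vaccine administration". The diary alarms in Protocol 5.6.16.1.1 match this, running "from Day 1 to Day 30 after Visit 5".
- **Other solicited events, and fever after doses 1-3.** The window is 7 days. Only events still ongoing are followed further, to resolution or Day 30 (Protocol 7.1.3 and the footnotes to Protocol Table 5). A new onset outside the window counts as unsolicited (Protocol glossary).

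For the three 30-day events, the solicited-event summaries in SAP 5.4.1.1 state that "the study period will be divided into the following intervals: 6 hours through Day 7, Day 8 through Day 30". SAP 5.4.2.2 does not mention that division.

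**The concern.** The diary is completed daily (Protocol 5.6.16.1) and is designed to prevent blank or incomplete entries (Protocol 10.2). A day without the event is therefore normally an observation, and the rule overrides it. An infant with a short fever just after vaccination and another short fever more than a week later is summarised as having one long fever covering both.

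Thirty days is long enough for two unrelated fevers, or for an early reaction to a vaccine given at Visit 5 followed by a later event. Fever is listed as an important identified risk of the study vaccine (Protocol 1.3.1), and Protocol 1.1 describes the fever as resolving soon after vaccination. Duration figures that count event-free days could make a short-lived reaction look prolonged in the study report.

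**Working it through.** The documents state no duration figure, so there is none to reproduce. The check applies the SAP formula to example diaries.

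**Definitions.** F and L are the first and last days on which the event is reported, and N is the number of days on which it is reported. Rule duration R = L − F + 1. Event-free days counted as event days E = R − N, with every diary day completed.

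**Example diaries**

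| Days with event | R | N | E |
|---|---|---|---|
| 1-3 (continuous) | 3 − 1 + 1 = 3 | 3 | 0 |
| 1-2 and 10-11 | 11 − 1 + 1 = 11 | 4 | 7 |
| 2 and 12 | 12 − 2 + 1 = 11 | 2 | 9 |
| 1 and 30 | 30 − 1 + 1 = 30 | 2 | 28 |

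The rule is correct for a continuous event and wrong only when the event stops and returns.

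**Largest possible overcount.** In a window of W days the extreme case is the event on Day 1 and Day W only, so E = W − 2.

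- 7-day window: 7 − 2 = 5.
- 30-day window: 30 − 2 = 28.

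Following ongoing events to Day 30 does not raise the first figure. An event on Day 1 that returns on Day 7 and continues to Day 30 gives R = 30 and N = 1 + 24 = 25, so E is still 5.

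**A middling case.** Take two separate 1-day episodes and assume that all non-adjacent placements are equally likely. N is 2 throughout.

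- 7-day window: 15 placements, total span 65 days, mean R = 65/15 = 4.33 days.
- 30-day window: 406 placements, total span 4,872 days, mean R = 4,872/406 = 12.0 days.

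**Could the arms differ?** Let e be the proportion with early fever, l the proportion with later fever (equal in both arms and independent of early fever) and g the event-free days between. The share of febrile infants whose episodes are merged is el/(e + l − el), and the days added to mean duration are g times that share. No document gives e, l or g for dose 4. All values below are assumptions, with g = 7.

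| Early fever, MenB+PCV v Placebo+PCV | Later fever, both arms | Merged share | Days added | Difference |
|---|---|---|---|---|
| 50% v 20% | 15% | 0.075/0.575 = 13.0% v 0.030/0.320 = 9.4% | 0.91 v 0.66 | about 0.26 |
| 50% v 20% | 5% | 0.025/0.525 = 4.8% v 0.010/0.240 = 4.2% | 0.33 v 0.29 | about 0.04 |
| 30% v 20% | 5% | 0.015/0.335 = 4.5% v 0.010/0.240 = 4.2% | 0.31 v 0.29 | about 0.02 |

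Under these conditions the difference runs from about a quarter of a day to almost nothing, depending wholly on inputs that the documents do not supply.

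**The case against.** The rule is explicit and pre-specified, and no two passages contradict each other. Duration is not an endpoint. The solicited-event endpoints are percentages of subjects (SAP 3), and SAP 6 says that the safety endpoints are descriptive. Late fever also remains visible elsewhere, because the post-dose-4 summaries are divided at Day 7/8 and day of onset is summarised. All of this stands and limits the weight of the point. It does not make the duration figure right, because pre-specification makes a rule reproducible, not accurate.

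A second objection is that first-to-last-day span bridges missed diary days. This is partly right. Non-compliance alerts (Protocol 5.6.16.1.1) and the compliance analyses in SAP 5.4.2.9 show that missed days are expected, and a bare count of event days is low when an entry is missing. But the rule does not distinguish a missed day from a day recorded as event-free.

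A third objection concerns remedies. Computing duration separately either side of Day 7/8 would turn a continuous fever on Days 6-9 into two 2-day events. Starting a new episode after one event-free day would split an illness on a single reading below 38.0°C. Both criticisms stand, so neither remedy is proposed.

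A reader might also infer that the rule biases duration against the study vaccine, since Protocol 1.1 says that "increased rates of fever were associated with rMenB+OMV NZ vaccination in the infant population". That sentence concerns infants generally. It gives no rates and nothing specific to dose 4 at 12 months, so neither the presence nor the size of a difference between arms can be established from the documents.

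**Conclusion.** The point holds as a limited one. Applied exactly as written, SAP 5.4.2.2 merges separate episodes. The overcount is at most 5 days in the 7-day windows and at most 28 days for fever, rash and parotid/salivary gland swelling after dose 4. The 11-day against 4-day example follows from the formula and needs no assumption beyond a completed diary.

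The effect is confined to the descriptive duration statistics. No percentage endpoint, severity grade, day of onset or hypothesis test changes. How much the reported figures move depends on how often events recur within 30 days, which the documents do not say.

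Two stronger conclusions are not supported. A greater overstatement in the MenB+PCV group rests on assumed fever rates. Nor can it be said that merged episodes will determine the reported maximum, since one long continuous event could do so. The median is also likely to move little if only a small share of febrile infants have two episodes.

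**What to change.** In SAP 5.4.2.2, for each solicited event, add the number of days on which the event was recorded and report it beside the existing span. Show the number of missing diary days between first and last report separately, so that a low count can be told apart from an incomplete diary. For the 30-day Visit 5 events (fever, rash, parotid/salivary gland swelling), name the day count as the main duration measure. Keep the span in the tables, and do not cut duration at Day 7/8.

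This needs a SAP wording change and some programming on data already collected daily. The cost is one extra set of summary rows, and a count that is slightly low where diary days are missing.

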### 5.4.2.3. Derivation rule for duplicates Solicited Adverse Events

If there are two reported assessments for the same solicited adverse event in FACE, the Investigator one will be used for the analysis.

#### 5.4.2.4. Combined Solicited and Unsolicited Adverse Events

The number (%) of subjects with all combined solicited (regardless of their duration) and unsolicited adverse events will be provided. Solicited adverse events will be coded by MedDRA as per the following codes:

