All AEs which do not fall into these categories are defined as non-serious. It should be noted that a severe AE need not be serious in nature and that an SAE need not, by definition, be severe. All SAEs will be evaluated by the investigator for relationship of the event to study vaccine.

7.1.3. **Solicited adverse events**

The term “reactogenicity” refers to solicited signs and symptoms (“solicited adverse events”) occurring in the hours and days following a vaccination, to be collected by the parent(s)/LAR(s) for 7 consecutive days (with ongoing solicited AEs collected until resolution or day 30, whichever occurs first), using a pre-defined Subject Diary.

Reactogenicity will be collected from all subjects after each vaccination visit (study Days 1, 61, 121 and 301). In addition, specific solicited system AEs (parotid/salivary gland swelling, fever and rash) will be collected for 30 days following the MMR and VV vaccine administration at Visit 5.

The following solicited adverse events are included in the Subject Diary. Each adverse event is to be assessed using the scoring system reported in the tables below.

The collected data will be entered into the Subject Diary. Please see Section [5.6.16.1](#) for more detail.

7.1.3.1. **Solicited local adverse events (*administration site event*)**

Solicited local AEs (*administration site event*) will be collected following each study vaccine, by site of administration.

- Hardness of skin at injection site (*Induration at injection site*),
- Swelling of skin at injection site (*Swelling at injection site*),
- Redness at injection site (*Erythema at injection site*),
- Tenderness or discomfort to the touch at injection site (*Tenderness at injection site*).

In the eCRF, solicited local AEs (*administration site event*) occurring within 30 minutes after vaccination are described as mentioned within brackets.

7.1.3.2. **Solicited systemic adverse events**

- Decreased eating (*Change in eating habits*),

- Increased sleepiness (*Sleepiness*),
- Vomiting/throwing up (*Vomiting*),
- Loose stools/diarrhea (*Diarrhea*),
- Irritability (*Irritability*),
- Persistent/continuous crying (*Persistent crying*),
- Rash (only after MMR and VV administration at Visit 5),
- Parotid/salivary gland swelling (only after MMR and VV administration at Visit 5),
- Fever, defined as body temperature $\geq 38.0^{\circ}\text{C}/100.4^{\circ}\text{F}^*$.

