##### *Local reactions*

Solicited symptom	Lower level term code	Corresponding Lower level term decode
INDURATION	10060708	Induration
SWELLING	10053425	Swelling at injection site
REDNESS	10022098	Redness at injection site
TENDERNESS	10043224	Tenderness

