##### *Systemic reactions*

Solicited symptom	Lower level term code	Corresponding Lower level term decode
CHANGE IN EATING HABITS	10063889	Oral intake reduced
SLEEPING MORE THAN USUAL	10020765	Hypersomnia
VOMITING	10047700	Vomiting
DIARRHOEA	10012727	Diarrhea
IRRITABILITY	10057224	Irritability post vaccinal
UNUSUAL CRYING	10011470	Crying abnormal
RASH	10037844	Rash
PAROTID GLAND swelling	10034028	Parotid swelling
FEVER	10016558	Fever

For clinicaltrials.gov and EudraCT posting purposes, a summary of combined solicited and unsolicited non-serious adverse events will be produced by System Organ Class and preferred terms and according to occurrence of each event.

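### SAP 5.4.2.4 codes two of the four solicited local reactions, induration and tenderness, to terms that do not name the injection site

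*SAP*

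**What the plan says.** SAP 5.4.2.4 provides a count and percentage of subjects with solicited and unsolicited events taken together. To put solicited reactions in the same tables as coded events, it fixes a MedDRA lower level term for each: "Solicited adverse events will be coded by MedDRA as per the following codes".

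The local-reaction list has four rows:

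- "SWELLING 10053425 Swelling at injection site"
- "REDNESS 10022098 Redness at injection site"
- "INDURATION 10060708 Induration"
- "TENDERNESS 10043224 Tenderness"

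The same section adds that, for posting on clinicaltrials.gov and EudraCT, "a summary of combined solicited and unsolicited non-serious adverse events will be produced by System Organ Class and preferred terms".

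Protocol 7.1.3.1 lists the same four reactions as solicited local events, collected by site of administration. Its short name for each carries the injection site; for tenderness it is "Tenderness at injection site". SAP Table 6, which grades these reactions, also places all four at the injection site.

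**The concern.** Four reactions of one kind follow two coding conventions, and the SAP gives no reason. Swelling and redness keep their site; induration and tenderness lose it, although both documents define them by it.

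At stake is how clearly the combined outputs can be read. Someone looking there for injection-site terms finds two of the four solicited local reactions under terms that name the site and two under terms that do not. One reaction may also be divided between rows, depending on how it reached the database. Protocol 1.1 reports that local reactions are frequent with this vaccine in infants, so these rows are unlikely to be sparse.

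**Working it through.** No sample size, power or alpha is involved and the plan states no figure to reproduce. The check is a term-by-term comparison, followed by tracing where the codes are used.

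**Step 1. Compare the terms.**

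| Reaction | Site named in Protocol 7.1.3.1 | Site named in SAP Table 6 | Term in SAP 5.4.2.4 | Site named in that term |
|---|---|---|---|---|
| Swelling | yes | yes | "Swelling at injection site" | yes |
| Redness | yes | yes | "REDNESS 10022098 Redness at injection site" | yes |
| Induration (hardness) | yes | yes | "INDURATION 10060708 Induration" | no |
| Tenderness | yes | yes | "TENDERNESS 10043224 Tenderness" | no |

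The protocol names the site for 4 of 4 reactions, SAP Table 6 for 4 of 4, and the coding list for 2 of 4.

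**Step 2. Find which outputs use the codes.** Two do: the combined solicited and unsolicited count, and the registry summary by System Organ Class and preferred term. The solicited tables by symptom and severity (SAP 5.4.1.1) and the duration and onset summaries (SAP 5.4.2.2) work from the named symptom and do not depend on these codes.

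**Step 3. See how the same reaction can enter by another route.** Unsolicited events are coded from the investigator's verbatim term (SAP 5.4.1.1). A local reaction can reach the adverse event page of the eCRF in several ways:

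- its onset falls outside the solicited window (Protocol glossary, unsolicited adverse event);
- it is first reported verbally at a visit (Protocol 10.2);
- it is medically attended, leads to withdrawal, or is serious (Protocol 7.1.3.3). A serious event would not appear in the non-serious registry summary.

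A verbatim entry that mentions the injection site could be coded to a site-specific term, while the same reaction from the diary is fixed to the bare term. That is a possible split between rows, and the documents do not allow its frequency to be estimated.

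**Step 4. Look for a remedy elsewhere.** SAP section 8 (changes from planned analyses) does not mention the coding. SAP Annex 1 contains only method references. The output and programming specification, which holds the mock tables, is not among the documents.

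**The case against.** The strongest case against is that little follows from the mismatch, and most of that case stands.

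- **Dictionary placement.** A reader might infer that the two reactions move to another preferred term or System Organ Class. The list gives only lower level terms and the documents do not reproduce the MedDRA hierarchy, so this cannot be shown. Only the wording of the assigned terms can.
- **Understatement in public.** A reader might infer that local reactogenicity is understated where the public sees it. The documents do not support that. Every induration and tenderness event stays in the combined table under its own name. Protocol 10.7 also commits to disclosing primary endpoint results, and those include the percentages with solicited local events. The combined summary is not the only public output.
- **Merging with unrelated events.** A reader might infer that the bare terms would absorb unsolicited tenderness or induration at other body sites. That depends on verbatim reports not yet coded, and nothing in the documents shows it would happen.
- **Group comparison.** The same list applies to both groups, so the coding rule itself does not favour either.
- **Table layout.** A label or footnote in the output specification could restore the site. That can be neither confirmed nor excluded.

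What the objection does not answer is the mismatch itself. The SAP fixes the codes in its own text, and if they are followed exactly, two of four local reactions are coded without a qualifier that both documents use to define them.

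**Conclusion.** The point holds as a coding inconsistency of minor weight. Two of the four solicited local reactions are coded to lower level terms without the injection site, apart from the other two, after each of the four vaccinations and in both groups. The outputs affected are the combined table and the registry summary. The count of subjects with any combined event does not change, and no objective or success criterion is touched.

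The conclusion rests on two assumptions: that the codes are applied as printed, and that the unseen output specification does not override them. It does not rest on any claim about preferred term or System Organ Class.

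**What to change.** In the local-reaction list of SAP 5.4.2.4, replace the induration and tenderness codes with injection-site-specific terms, as is already done for swelling and redness. Before finalising, check all four codes against the MedDRA version in use, including the preferred term and System Organ Class to which each leads. If the bare terms were chosen deliberately, say why in that section.

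The cost is two rows in a mapping list and a dictionary check. It needs no new data, no protocol amendment and no change to the main solicited tables.
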